10.1 Primary Efficacy Endpoint and Analysis

No primary efficacy endpoint is defined for this study.

10.2 Key Secondary Efficacy Endpoint(s) and Analysis

10.2.1 ADHD-RS-5 Child, Home Version

To assess long-term efficacy, ADHD-RS-5 Child, Home version will be administered to children aged 4-5 years and 6-12 years. Baseline ADHD-RS-5 total score is defined as the last valid assessment prior to taking the first dose of investigational product for Group B and as the baseline value from the antecedent study for Group A. The observed and change from baseline in ADHD-RS-5 total score will be summarized at each applicable visit using the number of subjects, mean, SD, median, minimum, maximum values, and 95% confidence interval. A corresponding line graph of mean change from baseline and associated 95% CI in ADHD-RS-5 total score by visit and treatment group of the antecedent studies and current treatment (SHP465) for each enrollment type will be presented.

The items in the ADHD-RS-5 will also be grouped into 2 subscales: hyperactivity/ impulsivity (9 items for hyperactivity/impulsivity) and inattentiveness (9 items for inattentiveness). Each subscale will be summarized descriptively at each applicable visit. A corresponding line graph of mean change from baseline and associated 95% CI in the ADHD-RS-5 subscale scores by visit and treatment group of the antecedent studies and current treatment (SHP465) for each enrollment type will be presented.

Summaries will be repeated by age group (4-5 years and 6-12 years), sex, race (white and non-white), and ethnicity sub-group.

ADHD-RS-5 scores, including individual, subscale, and total scores, will be listed for FAS.

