#### **4.3.2 Reasons for Discontinuation**

The reason for withdrawal must be determined by the investigator and recorded in the subject's medical record and source documents. If a subject is withdrawn for more than 1 reason, each reason should be documented in the source documents.

Reasons for discontinuation include but are not limited to:

- Adverse event
- Protocol violation
- Withdrawal by subject or parent/LAR
- Lost to follow-up
- Lack of efficacy
- Blood pressure and/or pulse criteria met
- Other (must be specified)

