10. EFFICACY ANALYSES

All efficacy analyses will be performed using the FAS. Efficacy data will be summarized descriptively and no formal statistical tests will be performed. Only post-baseline assessments from Visit 3 (Week 1) up to Visit 16 (Month 12) that were collected on or 2 days after the last dose of investigational product will be analyzed. Summarization will be by treatment group of the antecedent studies, current treatment (SHP465) for each enrollment type, and overall.

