10.2.2 CGI-I scores

The CGI-S scores will be collected at Baseline Visit (Visit 2) for subjects in Group B and at the Screening Visit (study SHP465-112) or the Baseline Visit (study SHP465-309) for subjects in Group A and summarized descriptively. The CGI-I will be summarized descriptively at each applicable visit using the number of subjects, mean, SD, median, minimum, and maximum values.

The CGI-I categories will also be dichotomized into 2 categories: "improved" and "not improved". The category of "improved" will include CGI-I scores of 1 ("very much improved")

and 2 ("much improved"). The category "not improved" will include all CGI-I scores >2 . Missing CGI-I scores will not be imputed. The observed and dichotomized CGI-I values will be summarized at each applicable visit, using number of subjects and percentages, as well.

Summaries will be repeated by age group (4-5 years and 6-12 years), sex, race (white and non-white), and ethnicity subgroups.

A corresponding bar chart showing the percentage of subjects improved by visit and treatment group of the antecedent studies and current treatment (SHP465) for each enrollment type will be presented. CGI-I values and CGI-S values will be listed for FAS and CGI-S will be also listed for the Safety Set.

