11. SAFETY ANALYSES

Safety data will be analyzed for the Safety Set by treatment group of the antecedent studies, current treatment (SHP465) for each enrollment type, and overall. Safety endpoints include the occurrence of TEAEs, vital signs (systolic and diastolic blood pressure, and pulse), height, weight, body mass index (BMI); clinical laboratory and ECG results, C-SSRS, and sleep questionnaires (PSQ and CSHQ). For each safety endpoint, the last value collected before the first dose of investigational product in this study will be used as baseline for all analyses of that safety endpoint. Except for adverse event data, only post-baseline assessments from Visit 2 (Week 0) up to Visit 16 (Month 12) that were collected on or 2 days after the last dose of investigational product will be analyzed. A Final on-Treatment Assessment (FoTA) will be defined as the last valid assessment obtained after Baseline and whilst on investigational product (on or before 2 days after the last dose date).

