11.3 Vital Signs (Including Height and Weight)

The averaged values of the 3 measurements collected for blood pressure and pulse at each visit will be used for all summaries and determination of PCIs. Summaries for vital signs will be presented by treatment group of the antecedent studies, current treatment (SHP465) for each enrollment type, and overall.

Descriptive statistics for vital signs (sitting systolic and diastolic blood pressure, pulse and weight) and their changes from baseline at each post-baseline visit and FoTA will be presented in a summary table. These summaries will also include BMI. BMI will be automatically

calculated using the height and weight collected at each visit. In the case of multiple assessments at post-baseline visits, the first readable value at the visit will be used in the summary tables.

Additionally, figures with the mean change from baseline \pm SD of the vital signs values (sitting systolic and diastolic blood pressure, and pulse) will be presented by visit for each treatment group of the antecedent studies and current treatment (SHP465) for each enrollment type.

Height, weight and BMI will also be converted to percentile values based on the subject's age and sex at each visit and summarized categorically (<5th, 5th to <95th, and \geq 95th) at each visit and at the FoTA. Post-baseline shifts in height, weight and BMI percentile category (<5th, 5th to <95th, and \geq 95th) from baseline will be summarized at each visit and at the FoTA. In addition, z-scores for weight and BMI will be based on the subject's age at each visit and will be summarized categorically (<-2, \geq -2 to <-1, \geq -1 to <1, \geq 1 to <2, and \geq 2) at each visit and at the FoTA. Percentiles and z-scores will be derived using the CDC growth charts ([Kuczmarski et al. 2002](#)). A SAS program for the 2000 CDC Growth Charts will be used to derive the percentiles and z-scores (www.cdc.gov/nccdphp/dnpao/growthcharts/resources/sas.htm).

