11.4 Electrocardiogram (ECG)

Electrocardiogram (ECG) data will be summarized by treatment group of the antecedent studies, current treatment (SHP465) for each enrollment type, and overall. ECG results and change from baseline will be summarized at each visit and at the FoTA. If there are multiple assessments for the interpretation at any visit, the worst interpretation will be used in the summary tables. For the interval parameters at post-baseline visits, the first readable result will be used if there are multiple assessments.

For the ECG interval parameters, baseline is defined as the average of all valid ECG measurements as the last assessment obtained prior to the first dose of the investigational product. For the ECG interpretation, baseline will be the ECG with the worst interpretation obtained at the baseline Visit (Visit 2), providing this is prior to the first dose of the investigational product.

PCI criteria will be applied to all ECG data at each visit including any repeat/unscheduled assessments and presented by visit. PCI criteria are defined in [Table 10](#) for Age 4-5 years or if they meet the criteria in [Table 11](#) for Age 6-12 years.

Table 10 Criteria for Potentially Clinically Important ECG Values for Age 4-5 Years

ECG Parameter	Unit	Observed Value		Change from Baseline	
		Lower Limit	Higher Limit	Lower Limit	Higher Limit
ECG Result	-	-	Abnormal (core lab) and Clinically significant from investigator	-	-
Heart Rate	Beats/minute	<55	>130	Decrease >15	Increase >15
PR Interval	msec	-	≥200	-	-
QT Interval	msec	-	≥440	-	≥30 and <60 ≥60
QTcF Interval	msec	-	≥440 and <480 ≥480 and <500 ≥500	-	≥30 and <60 ≥60
QTcB Interval	msec	-	≥440 and <480 ≥480 and <500 ≥500	-	≥30 and <60 ≥60
QRS Interval	msec	-	≥90	-	-
Rhythm	-	-	Any rhythm other than sinus rhythm*	-	-

Age is calculated from the informed consent date from antecedent studies for Group A and from the informed consent date from SHP465-308 for Group B.

Table 11 Criteria for Potentially Clinically Important ECG Values for Age 6-12 Years

ECG Parameter	Outlier Criteria
ECG result	Shift from a normal baseline to an abnormal finding or from an abnormal baseline to a new abnormal finding
Heart rate	≤50 beats/minute* or ≥100 beats/minute*
PR interval (increase)	≥200 msec*
QRS interval	≥120 msec*
QTcF/QTcB	≥450 msec* and <480 msec* ≥480 msec* and <500 msec* ≥ 500msec*
QT/QTc from Baseline	≥30 msec* and <60 msec* ≥60 msec*

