18.3 Association of Early Termination Assessments to Scheduled Visits

For purposes of reporting early termination assessments during the study, each early termination visit will be assigned the next nominal visit number after the last completed visit. This rule applies to both efficacy variables (e g , ADHD-RS-5 - Child, Home Version total score) and safety variables (e g , vital signs) except for the lab data, which will be analyzed and/or summarized by visit.

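### Efficacy is summarised only as observed cases by visit; a supplementary final on-treatment row, already defined for safety, would show how all treated children ended up

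*SAP*

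**What the plan says.** **Efficacy.** SAP 10.2.1 states of the ADHD-RS-5: "The observed and change from baseline in ADHD-RS-5 total score will be summarized at each applicable visit". The subscales are also by visit, and the line graphs plot mean change with a 95% CI by visit. SAP 10.2.2 tabulates CGI-I by visit, both as a score and as improved or not improved, with a bar chart by visit, and adds: "Missing CGI-I scores will not be imputed". Protocol 9.8 also plans descriptive by-visit summaries of observed data and leaves missing-data rules to the SAP.

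**Missing data.** The only ADHD-RS-5 imputation, in SAP 18.2, fills one missing item within a subscale. It cannot fill a missed visit. For children who stop early, SAP 18.3 says "each early termination visit will be assigned the next nominal visit number after the last completed visit", and this covers efficacy as well as safety variables.

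**Safety.** SAP 11 supplies an end-of-treatment summary: "A Final on-Treatment Assessment (FoTA) will be defined as the last valid assessment obtained after Baseline and whilst on investigational product", with a cut-off 2 days after the last dose. SAP 11.3 reports vital signs and "their changes from baseline at each post-baseline visit and FoTA". SAP 11.4 says "ECG results and change from baseline will be summarized at each visit and at the FoTA". Neither efficacy section uses FoTA.

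**The concern.** The secondary objectives are to describe long-term efficacy, so a reader will look to the later visits. Who is present at those visits may depend on response. Protocol 4.3.2 lists "Lack of efficacy" among the reasons for discontinuation, Protocol 4.3 does not replace children who leave, and the dose is fixed. If those who leave have done less well, the rows after their departure average over better responders, and a curve can rise without any child improving.

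This matters for interpretation because SAP 1 reports that study SHP465-309 found 6.25 mg not efficacious at ages 6 to 12. An open-label curve that climbs over months could be read against that result when part of the climb comes from a change in who is being averaged. The planned tables contain no row that would let a reader check.

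**Working it through.** **Step 1: follow one child through the tables.** Take a child who completes Visit 7 (Month 3) and then stops.

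- Visits 3 to 7: counted in each row.
- Early-termination visit: assigned to Visit 8 by SAP 18.3 and counted there once, if it falls inside the on-treatment window.
- Visits 9 to 16: absent. No rule carries the score forward or models it.

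The last score is therefore used, but children who stop at different times have theirs scattered over different visit rows. No row gathers them.

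**Step 2: compare efficacy with safety.**

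| Measure | By visit | FoTA |
|---|---|---|
| Vital signs, weight, BMI (SAP 11.3) | yes | yes |
| ECG (SAP 11.4) | yes | yes |
| ADHD-RS-5 total and subscales (SAP 10.2.1) | yes | no |
| CGI-I (SAP 10.2.2) | yes | no |

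**Step 3: what could the difference amount to?** The documents give no dropout rate, expected change or SD, and the sample size is not statistically based, so there is no planned figure to reproduce. What follows is illustration only.

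Let r be the fraction still present at a visit, S the mean change in those present, and L the mean last on-treatment change in those who have left. Ignoring the few early-termination scores mapped to that same visit:

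- observed-case mean = S
- all-subject mean = r × S + (1 − r) × L
- difference = (1 − r) × (L − S)

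Inputs for r at Month 6:

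- SAP 2.5 pairs about 80 enrolled with 60 completing 6 months: 60/80 = 0.750.
- Protocol 9.6 pairs about 145 enrolled with the same 60: 60/145 = 0.414.

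Assumed input: L − S of 0, 5 or 10 points on the 0 to 54 scale (leavers' change less favourable).

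| r | gap 0 | gap 5 | gap 10 |
|---|---|---|---|
| 0.750 | 0 | 0.25 × 5 = 1.25 | 0.25 × 10 = 2.5 |
| 0.414 | 0 | 0.586 × 5 = 2.9 | 0.586 × 10 = 5.9 |

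For example, at r = 0.750 with S = −15 and L = −5, the visit row shows −15, while the all-subject mean is 0.75 × (−15) + 0.25 × (−5) = −12.5.

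**Step 4: can an efficacy FoTA be built from the SAP as it stands?** Almost. SAP 10 limits efficacy data to assessments "that were collected on or 2 days after the last dose of investigational product will be analyzed". Read literally, that keeps only assessments on the last-dose day or after it. The FoTA definition in SAP 11 reaches back from 2 days after the last dose. The two need one wording. In addition, the FAS definition in SAP 4.4 has no such window, so a child whose only post-dose ADHD-RS-5 falls outside it would be in the FAS without a FoTA.

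**The case against.** The case for leaving the plan alone has real content.

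- **Efficacy is descriptive.** There is no primary efficacy endpoint, no formal test and no control arm, and the SAP follows Protocol 9.8. This stands: no error rate or decision rule is affected. It limits the point to reporting and interpretation.
- **Attrition is already visible.** The tables give the number of subjects at each visit, SAP 5 summarises discontinuation reasons and visit completion, and individual scores are listed. This also stands. A reader can see that children left, but would have to compute from listings how they fared overall. The figures carry no stated n.
- **Bias in favour of the drug is not shown.** Lack of efficacy is one of seven listed discontinuation reasons. Protocol 6.2.3 attaches no discontinuation action to an ineffective response. Children cut off by the sponsor's stop left because of the calendar, which reduces n without necessarily selecting responders. This stands in full.
- **FoTA is an imperfect measure of long-term efficacy.** It pools a Week 1 score with a Month 12 score, especially after an early stop. True, which is why it should supplement the by-visit rows and be shown with duration of exposure.

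**Conclusion.** The gap is real and modest. Efficacy is reported only on whoever remains at each visit, and nothing summarises FAS subjects at the end of their treatment, although the SAP already does this for vital signs and ECG. If leavers responded less well, late rows can look better than the whole group did. Under the assumed 5 to 10 point gap, the Month 6 difference is 1.3 to 2.5 points at 75% retained and 2.9 to 5.9 points at 41%. It is zero if leavers and stayers do not differ.

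Three stronger readings are tempting and are not supported:

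- A reader might infer that the late-visit results will overstate efficacy. That needs departure to be driven mainly by non-response. The documents give no such rate, and the early stop makes part of the attrition administrative, so neither direction nor size can be computed.
- A reader might take 60/145 as an expected 41% retention. It is not a forecast: 60 is a minimum to be ensured, and the protocol's amendment summary says the 145 was set to accommodate enrolment to date and rollover from SHP465-112.
- A reader might infer that leavers' final scores are discarded. SAP 18.3 keeps them, once each, subject to the on-treatment window.

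This is a cheap improvement to reporting and does not invalidate the planned analysis.

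**What to change.** 1. In SAP 10, restate the assessment window so that it agrees with the FoTA definition in SAP 11 (assessments up to and including 2 days after the last dose).
2. Keep all by-visit rows. In SAP 10.2.1 add a supplementary FoTA row for change in ADHD-RS-5 total and subscale scores. In SAP 10.2.2 add one for the number and percentage improved on CGI-I.
3. On the figures, add a separate FoTA point or bar, not joined to the visit curve, and print n under each visit.
4. State how many FAS subjects have no in-window score and so no FoTA.
5. Footnote that FoTA mixes treatment durations, and give the exposure duration beside it.

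The cost is one row per table and a small change to the figures, using data already collected and a definition already in the SAP. The downside is the mixture of durations, which items 2 and 5 address by keeping FoTA supplementary and labelled.

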10.2.2 CGI-I scores

The CGI-S scores will be collected at Baseline Visit (Visit 2) for subjects in Group B and at the Screening Visit (study SHP465-112) or the Baseline Visit (study SHP465-309) for subjects in Group A and summarized descriptively. The CGI-I will be summarized descriptively at each applicable visit using the number of subjects, mean, SD, median, minimum, and maximum values.

The CGI-I categories will also be dichotomized into 2 categories: "improved" and "not improved". The category of "improved" will include CGI-I scores of 1 ("very much improved")

and 2 ("much improved"). The category "not improved" will include all CGI-I scores >2 . Missing CGI-I scores will not be imputed. The observed and dichotomized CGI-I values will be summarized at each applicable visit, using number of subjects and percentages, as well.

Summaries will be repeated by age group (4-5 years and 6-12 years), sex, race (white and non-white), and ethnicity subgroups.

A corresponding bar chart showing the percentage of subjects improved by visit and treatment group of the antecedent studies and current treatment (SHP465) for each enrollment type will be presented. CGI-I values and CGI-S values will be listed for FAS and CGI-S will be also listed for the Safety Set.

10.3 Exploratory Efficacy Endpoint(s) and Analysis

No exploratory efficacy endpoint is defined for this study.

11. SAFETY ANALYSES

Safety data will be analyzed for the Safety Set by treatment group of the antecedent studies, current treatment (SHP465) for each enrollment type, and overall. Safety endpoints include the occurrence of TEAEs, vital signs (systolic and diastolic blood pressure, and pulse), height, weight, body mass index (BMI); clinical laboratory and ECG results, C-SSRS, and sleep questionnaires (PSQ and CSHQ). For each safety endpoint, the last value collected before the first dose of investigational product in this study will be used as baseline for all analyses of that safety endpoint. Except for adverse event data, only post-baseline assessments from Visit 2 (Week 0) up to Visit 16 (Month 12) that were collected on or 2 days after the last dose of investigational product will be analyzed. A Final on-Treatment Assessment (FoTA) will be defined as the last valid assessment obtained after Baseline and whilst on investigational product (on or before 2 days after the last dose date).

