### 3 STUDY DESIGN

#### 3.1 Study Design and Flow Chart

This study is a Phase 3, long-term, open-label, multicenter, safety, and tolerability study in children (aged 4-12 years, inclusive, at the time of consent was obtained in the antecedent study [SHP465-112 or SHP465-309] or at the time of consent into this study if directly enrolled) with ADHD.

Approximately 145 subjects will be enrolled into this study. Subjects enrolled in this study will be divided into 2 groups based on participation in antecedent studies as follows:

[figure not shown]
- Subjects in Group A are those who have been rolled-over from antecedent studies (SHP465-112 or SHP465-309). These subjects do not need additional screening and washout procedures.
- Subjects in Group B will be directly enrolled subjects who will be required to undergo full screening and washout before enrollment.

Subjects in Group A will participate in the following 2 study periods: (1) treatment period and (2) safety follow-up. Subjects in Group B will participate in the following 3 study periods: (1) screening and washout, (2) treatment period, and (3) safety follow up.

[figure not shown]
For subjects in Group A, the last visit of the antecedent study, SHP465-112 or SHP465-309, will serve as the baseline visit (Visit 2) for this study. For subjects in Group B, a screening visit will precede a washout period.

The investigator or designee must obtain written informed consent from the subjects, if applicable, and the subject's parent/legally authorized representative (LAR) before any protocol-related procedure is performed. Procedures performed at each visit for all subjects are defined in the Study Schedules.

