#### 6.2.3 Dosing

Dosing should begin at 7:00 AM ( $\pm 2$  hours) on the morning after the baseline visit (Visit 2). The parent/LAR responsible for dosing will be instructed to dispense 1 capsule to the subject daily in the morning throughout the study, at approximately the same time each day. The same parent/LAR should be available daily to dispense the dose of investigational product for the study duration.

SHP465 may be administered in 1 of the following ways:

- Swallow SHP465 capsule whole, or
- Open capsule and sprinkle the entire contents on applesauce

The sprinkled applesauce should be consumed immediately; it should not be stored. Subjects should take the sprinkled applesauce in its entirety without chewing. The dose of a single capsule should not be divided. The empty capsule shells should be discarded.

Subjects will be treated with SHP465 at 6.25 mg.

The investigator will categorize subject response into 1 of the following 3 conditions, along with the associated actions:

- **Intolerable response** (ie, subject experiences intolerable side effects): If this lower dose also produces an intolerable effect, the subject should be discontinued from the study.
- **Ineffective response** (ie, subject has not achieved at least a 30% reduction in ADHD-RS-5 Child, Home Version total score from the baseline visit [Visit 2] and a CGI-I score of 1 or 2).
- **Acceptable response** (ie, subject has achieved at least a 30% reduction in ADHD-RS-5 Child, Home Version total score from the baseline visit [Visit 2] and a CGI-I score of 1 or 2 with tolerable side effects): This response suggests that an optimal dose has been achieved and the subject should maintain this dose for the remainder of the study.

If the subject experiences unacceptable tolerability, in the opinion of the clinician, the subject will be discontinued.

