2. STUDY DESIGN

2.1 General Study Design

Study SHP465-308 is a Phase 3, open-label, multicenter, 12-month safety and tolerability study of SHP465 in children (aged 4-12 years, inclusive, at the time of consent was obtained in the antecedent study [SHP465-112 or SHP465-309] or at the time of consent into this study if directly enrolled) with ADHD.

Approximately 80 subjects will be enrolled into this study. Subjects enrolled in this study will be divided into 2 groups based on participation in antecedent studies as follows:

- Subjects in Group A are those who have been rolled over from antecedent studies (SHP465-112 or SHP465-309). These subjects do not need additional screening and washout procedures.
- Subjects in Group B will be directly enrolled subjects who will be required to undergo full screening and washout procedures before first dose.

Antecedent study SHP465-112 is a Phase 1 study in subjects aged 4-5 years who were administered 6.25 mg SHP465. Antecedent study SHP465-309 is a Phase 3 study in subjects aged 6-12 years who were randomized to either 6.25 mg SHP465 or placebo.

For subjects in Group A, the baseline defined in the antecedent study, SHP465-112 or SHP465-309, will serve as the baseline visit (Visit 2) for analyses of this study. For subjects in Group B, a screening visit will precede a washout period. Data will be summarized using the following layouts:

- For full analysis, data will be summarized using the following 5 columns:
 - Antecedent Study:
 - Group A 112 SHP465 6.25mg
 - Group A 309 Placebo
 - Group A 309 SHP465 6.25mg
 - Direct Enrollment: Group B SHP465 6.25mg
 - Total
- For full analysis by-age group summaries, data will be summarized using the following 3 columns:
 - Group A Antecedent Study
 - Group B Direct Enrollment
 - Total

For all subjects in Group A and Group B, SHP465 will be administered as a daily morning dose of 6.25 mg in the treatment of ADHD.

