7. DEMOGRAPHIC AND OTHER BASELINE CHARACTERISTICS

7.1 Demographic and Other Baseline Characteristics

Descriptive summaries of demographic and baseline characteristics will be presented for the Safety Set and FAS by treatment group of the antecedent studies (SHP465 or Placebo), current treatment of SHP465 for each enrollment type (rolled over or direct enrollment), and current treatment of SHP465 for overall.

The following demographic characteristics will be summarized in the following order in the tables: age, age group (4-5 years, 6-12 years), sex, ethnicity, race, weight, height, and body mass index (BMI). In addition, other baseline characteristics such as years since diagnosis of ADHD, baseline ADHD-RS-5 Child, Home Version total score for children aged 4-5 years and for children aged 6-12 years, and baseline Clinical Global Impressions-Severity (CGI-S) will be summarized. Baseline is defined as the last assessment before the first administration of the investigational product for Group B and as the non-missing assessment for the last visit of the antecedent study for Group A.

Age, weight, height, BMI, years since diagnosis of ADHD, ADHD-RS-5 Child, Home Version total score for children aged 4-5 years and for children aged 6-12 years will be summarized as continuous variables using number of subjects, mean and SD, median, and minimum and maximum values. Sex, ethnicity, race, and baseline CGI-S will be summarized as categorical variables using number of subjects and percentages for each category. For Group A, all summarized values will be taken from the baseline value from antecedent studies, while for Group B, summarized values will be taken from the Screening Visit (Visit 1), except for baseline ADHD-RS-5 Child, Home version Total Score and baseline CGI-S, which will be taken from the Baseline Visit (Visit 2). In addition, baseline weight and baseline height will be summarized in both conventional and international system of units.

Age will be calculated as the difference between date of birth (DOB) and earliest date of informed consent (DINFC) (i.e., consent date from antecedent studies for Group A and consent date from SHP465-308 for Group B), truncated to months, using the following:

- $\text{Age} = \text{floor}(\text{intck}(\text{'month'}, \text{DOB}, \text{DINFC}) - (\text{day}(\text{DINFC}) < \text{day}(\text{DOB}))) / 12$

BMI will be calculated using one of the following:

- $\text{Weight in pounds} * 703 / (\text{Height in inches})^2$

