17. CHANGES TO ANALYSES SPECIFIED IN PROTOCOL

Not applicable.

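### The SAP gives Group A two different baselines without labelling them, so safety change for SHP465-treated rollovers is probably measured from an on-drug value

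*SAP*

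**What the plan says.** **Protocol 3.1:** "For subjects in Group A, the last visit of the antecedent study, SHP465-112 or SHP465-309, will serve as the baseline visit (Visit 2". Protocol 6.2.3 and 7.1.1.3 start dosing on the following morning, and Group A has no washout.

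**SAP 2.1:** "For subjects in Group A, the baseline defined in the antecedent study, SHP465-112 or SHP465-309, will serve as the baseline visit (Visit 2". The sentence applies this to the analyses of the study and does not limit it to efficacy.

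**SAP 7.1** gives two rules for Group A. One sentence defines baseline "as the non-missing assessment for the last visit of the antecedent study for Group A". A later one reads "For Group A, all summarized values will be taken from the baseline value from antecedent studies".

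**SAP 10.2.1** defines the ADHD-RS-5 baseline "as the baseline value from the antecedent study for Group A".

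**SAP 11** sets one rule covering all the safety measures: "the last value collected before the first dose of investigational product in this study will be used as baseline for all analyses". SAP 11.5.1 makes an exception for the C-SSRS, which is compared with the antecedent study's Baseline version. SAP 11.4 (ECG intervals) and 18.4 refer to the first dose or start of investigational product without saying in which study.

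**SAP 17**, headed "CHANGES TO ANALYSES SPECIFIED IN PROTOCOL", carries only a not-applicable entry.

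**The concern.** The primary objective is the long-term safety of SHP465, and blood pressure, pulse and weight are named in it. Change means and change-based flags for potentially clinically important (PCI) values depend directly on the baseline. Those flags are a blood pressure rise above 10 mmHg, a weight loss of at least 7%, and a pulse rise above 15 bpm (sufficient alone at ages 4-5, but only together with at least 100 bpm at ages 6-12).

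If a child arrives at Visit 2 already on SHP465, change from Visit 2 cannot show an effect that began in the antecedent study and persists.

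The written rules also give one child two baselines. Under the second rule in SAP 7.1, the baseline weight in the demographic table is not the weight behind the 7% flag.

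For efficacy the problem runs the other way: in SHP465-309 placebo rollovers, part of the reported ADHD-RS-5 change predates SHP465.

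**Working it through.** **1. The definitions side by side (Group A)**

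| Place | Antecedent baseline | Last antecedent visit (Visit 2) |
|---|---|---|
| Protocol 3.1 | | yes |
| SAP 2.1 | yes | |
| SAP 7.1 | yes (later sentence) | yes (definition) |
| SAP 10.2.1, ADHD-RS-5 | yes | |
| SAP 11, safety | | yes, in practice |

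Two definitions are in play. For Group A safety, SAP 2.1 and SAP 11 cannot both hold as written.

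**2. Is Visit 2 on drug?** SAP 2.1 says SHP465-112 gave 6.25 mg SHP465 and SHP465-309 randomized to 6.25 mg or placebo. Protocol 4.1 requires rollovers to have completed the antecedent treatment period. Rollover is on the day of the final antecedent visit, without washout, and dosing resumes the next morning. Protocol 7.2.3.4 describes an antecedent dose maintenance visit. Together these make an on-drug value probable for 112 and 309-SHP465 rollovers. The antecedent protocols and the interval since the last antecedent dose are not supplied, so it remains an inference.

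**3. Effect on mean safety change.** Let *e* be the effect present at Visit 2. Then change from Visit 2 = (change from pre-SHP465 value) − *e*. The column mean falls by *e*. The Total mean falls by *p* × *e*, where *p* is the share of subjects on drug at Visit 2.

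Protocol 1.2 reports mean rises of 2-4 mmHg and 3-6 bpm, from a programme citing 12.5 mg and above. The effect at 6.25 mg and the value of *p* are not given. If those effects were fully present at Visit 2:

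| Assumed *p* | Blood pressure, *p* × 2 to *p* × 4 | Pulse, *p* × 3 to *p* × 6 |
|---|---|---|
| 0.25 | 0.5-1.0 mmHg | 0.75-1.5 bpm |
| 0.50 | 1.0-2.0 mmHg | 1.5-3.0 bpm |
| 0.75 | 1.5-3.0 mmHg | 2.25-4.5 bpm |

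**4. Effect on a change-based flag at one visit.** With normally distributed change, P(change > *c*) = 1 − Φ((*c* − *m*)/SD), where *m* = 0 from an on-drug baseline and *m* = *e* from a pre-SHP465 baseline. The SDs are assumed, and the smallest effects are assumed to allow for the lower dose.

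| Flag | SD | On-drug baseline | Pre-SHP465 baseline |
|---|---|---|---|
| BP rise > 10 mmHg, *e* = 1 to 4 | 6 | 4.8% | 6.7-15.9% |
| | 8 | 10.6% | 13.0-22.7% |
| | 10 | 15.9% | 18.4-27.4% |
| Pulse rise > 15 bpm alone (ages 4-5), *e* = 1.5 to 6 | 8 | 3.0% | 4.6-13.0% |
| | 10 | 6.7% | 8.9-18.4% |
| | 12 | 10.6% | 13.0-22.7% |

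The blood pressure gap is about 2 to 12 percentage points.

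**5. What the SAP will actually tabulate.** SAP 11.3 counts subjects with at least one post-baseline PCI value, and Visits 3 to 16 are 14 visits. Take SD of change 8 and *e* = 3, with independent, equal visit errors (SD 8/√2 = 5.66), including one in the baseline. The chance of at least one rise above 10 mmHg is then about 66% against 47%, compared with 19.1% against 10.6% at one visit. The direction is the same and the levels are very different, so the step 4 rates do not describe the SAP's tables.

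**6. Efficacy.** For a 309-placebo rollover under SAP 10.2.1, ADHD-RS-5 change = (visit − Visit 2) + (Visit 2 − antecedent baseline). The second term arose on placebo and enters one for one. SAP 10.2.1 repeats these summaries by age, and SAP 2.1 gives by-age summaries a single Group A column. SHP465-309 supplies the 6-12 year olds, so that column merges its placebo and SHP465 rollovers.

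**The case against.** The strongest reply is that SAP 11 is explicit and specific. Read as specific over general, it leaves one baseline for safety change, and SAP 10.2.1 and 10.2.2 show a consistent preference for antecedent values in efficacy. On that reading, 2.1 and 7.1 are general sentences that were never aligned. This largely stands: a reader might infer that the safety baseline is undetermined, and the documents do not go that far. What remains is that 2.1 and 7.1 contradict the rule and that the split is not labelled.

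A reader might also set SAP 10.2.1 against Protocol 6.2.3, where an acceptable response requires that the "subject has achieved at least a 30% reduction in ADHD-RS-5 Child, Home Version total score from the baseline visit [Visit 2" visit. That is a site response category in a fixed-dose study, not an analysis definition. Protocol 3.1 is the text that SAP 2.1 departs from.

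Change from Visit 2 is a valid description of change within SHP465-308, and the five-column layout keeps the antecedent arms apart. Both points stand. Observed-value PCI limits, the blood pressure and pulse percentile tables, and observed growth percentiles do not depend on baseline.

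A pre-SHP465 baseline has limits too. A given visit would represent longer exposure for SHP465-treated rollovers than for the others. Rollovers are also selected for completing antecedent treatment without a clinically significant TEAE as Protocol 4.1 defines it, so the added tables would not recover an unselected drug effect.

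**Conclusion.** The point holds as a conflict in the text with a probable, unquantified consequence. SAP 2.1, 7.1, 10.2.1 and 11 need reconciling, and SAP 17 should record the departure from Protocol 3.1.

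For 112 and 309-SHP465 rollovers, the change-based safety results omit whatever effect was present at Visit 2. This rests on the on-drug inference and on the effect persisting. The illustrative figures further assume the SDs and a constant effect, and the documented effect sizes come from higher doses.

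Three stronger readings are not supported. Visit 2 is not documented to be on drug. No understatement of the Total PCI percentages can be given, because the share of SHP465 rollovers and the repeat-visit correlation are not stated. And although the by-age ADHD-RS-5 tables merge the two 309 arms, the same cannot be said of safety change: SAP 11.3 specifies no by-age change tables, and the table templates are in a separate document.

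All summaries are descriptive, so no test result is at stake. Severity is minor to should-fix.

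**What to change.** 1. Reconcile SAP 2.1, 7.1, 10.2.1 and 11 around two named baselines. The **SHP465-308 baseline** is Visit 2. The **pre-SHP465 baseline** is the antecedent baseline for 112 and 309-SHP465 rollovers, Visit 2 for 309-placebo rollovers, and the existing pre-dose baseline for Group B. State in every table which one is used, align the wording of 11.4 and 18.4, and record the departure from Protocol 3.1 in SAP 17.
2. Keep change from Visit 2. For 112 and 309-SHP465 rollovers with an antecedent pre-treatment value, add change from the pre-SHP465 baseline for blood pressure, pulse and weight, including the change-based PCI flags, by antecedent arm. Do not pool this by visit into Total, or else label the pooled column as mixing lengths of exposure. Footnote the selection of rollovers.
3. Show ADHD-RS-5 change from both baselines, and split 309 Placebo from 309 SHP465 in the by-age table for ages 6-12.

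The cost is SAP wording, one extra set of descriptive tables, and a merge of antecedent blood pressure and pulse records, which the SAP does not say it already draws. No new data are collected from subjects, and the protocol's monitoring rules are left untouched.
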